### **3.1b Rationale for this study**

Prior to conducting a future definitive trial, current Medical Research Council (MRC) guidelines for the development of complex interventions recommend conducting preliminary research to address areas of uncertainty, thereby informing the design and conduct of future research.

Our attempts to estimate the number of patients with an acute LPD matching our eligibility criteria attending the John Radcliffe trauma services has been limited by insufficient information available in the patient's medical records. This study aims to address this by determining how many patients with a LPD diagnosis satisfy our eligibility criteria.

Determining the recruitment rates will help estimate the duration of recruitment required for future studies. This is important given the difficulty in recruitment of participants to previous trials of conservative interventions for this condition in the UK.

As outlined previously, there is a paucity of evidence to inform the content of rehabilitation programmes after a LPD. There has been only one published Randomised controlled trial (RCT) comparing different exercise interventions which showed no clinically significant difference between general quadriceps strengthening exercise compared to vastus medialis specific strengthening exercise in a cohort of first-time LPD patients. Of note, there was an attrition rate of 52%, significantly limiting the utility of the results. The reasons for this are unknown but suggest aspects of the study design were not acceptable to the participants. Therefore, determining the acceptability of our intervention and data collection methods before a future definitive trial is important.

The poor reporting of interventions has been highlighted in a review of non-operative treatment for LPD. This makes it difficult to ascertain if the exercise interventions complied with current guidelines to optimise muscle strength. There was also wide variability in the exercises used. Only one study incorporated a running exercise into their programme and none reported using hopping, change of direction or sports specific exercises, or were inadequately described to determine if they did. This is particularly concerning as these are activities this patient cohort perceive to make their patella unstable and the majority of LPDs occur during sporting activities.

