## **SECTION 4.6 Sample size**

### **4.6a Target sample size**

Data we collected from the John Radcliffe trauma service for 2017 conservatively estimates 31 LPD patients match our eligibility criteria and 51 LPD patients are of unknown eligibility, due to the required information not being available in the patient's medical records. Of those of unknown eligibility, 23 are due to the direction of dislocation not being reported. As medial patellar dislocations are exceedingly rare a conservative estimate would be 54 eligible participants per year and 27 for our planned recruitment period of 6 months.

We aim to recruit 15 participants over 6 months. Recruitment will cease at the end of the designated recruitment period of 6 months or earlier if the target of 15 participants is achieved.

Previous trials in the UK investigating conservative interventions for this condition have reported low recruitment rates but not explicitly stated what these rates were. This makes it difficult to estimate recruitment rates for this study and why it forms one of our primary objectives. We feel a recruitment target of 15 participants is feasible due to our conservative estimate of eligible participants and the broader inclusion criteria in our study compared to previous studies.

As this is a feasibility study, no power calculation has been performed. A sample size of 15 is a pragmatic choice. This has been used for a study similar to ours, a single group prospective study investigating the acceptability and feasibility of exercise for patients with endometrial cancer.

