General health status	EQ-5D-5L	Baseline, 3 months post first physiotherapy session
Intervention delivery	Duration from LPD to first physio session, initial injury management, number of physiotherapy sessions attended, number of physiotherapy appointments participants unable to attend/did not attend, duration of the intervention from enrolment to discharge, exercises and dose of exercise	Completion of intervention

	prescribed from treatment logs completed by therapists	
Harms	Patient and staff reported adverse events including any recurrent patellar dislocation, subsequent listing for knee surgery for mechanical instability and any increases in pain or swelling resulting from the exercise intervention lasting > 1 week	From beginning of intervention to 3 months post first physiotherapy session

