### **5.2b Data storage during and after the study**

All study documents will be stored securely in locked filing cabinets accessible by study staff and authorised personnel only. Any personal details (e.g. addresses for postal questionnaires) will be held separately to outcome data. Electronic data will be password protected and stored on computers with swipe card access for authorised personnel only.

Follow-up outcome data will be collected from participants via stamped pre-addressed envelope to *CF* at the physiotherapy trauma outpatient department at the John Radcliffe Hospital

Any study related data transferred from *CF* to his supervisors will refer to participants by their unique code/number only and be transferred using an encrypted memory stick device. This data will be deleted as soon as it is no longer needed.

Personal data will be stored for up to 12 months after the study and then destroyed. Anonymised research data will be stored securely at City, University of London for 10 years after the study has finished.

Oxford University Hospital NHS Foundation Trust will collect information participant information from their medical records for this research study in accordance with our instructions. Oxford University Hospital NHS Foundation Trust will use the participant's name, NHS number and contact details to contact participants about the research study, make sure that relevant information about the study is recorded for their care, and to oversee the quality of the study. Individuals from City, University of London and regulatory organisations may look at the participant's medical and research records to check the accuracy of the research study. Oxford University Hospital Foundation Trust will pass these details to City, University of London along with the information collected from the participant and/or their medical records. The only people in City, University of London who will have access to information that identifies participants will be people who need to contact the participants to monitor the conduct of the study or audit the data collection process. The people who analyse the information will not be able to identify participants and will not be able to find out the participant's name, NHS number or contact details.

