## **SECTION 5.3 Statistical methods**

### **5.3a Statistical Methods for analysing primary and secondary outcomes**

Statistical methods and results will be reported, where possible, in accordance with SAMPL guidelines. All analyses will be conducted using the latest version of SPSS (IBM Corp. Armonk, NY).

Eligibility, recruitment, acceptability and adherence will be described using descriptive statistics and expressed as integers and percentages where relevant.

Tegner Activity scores will represent ordinal data. Baseline and 3 months post 1st physiotherapy session scores will be described using descriptive statistics using median and inter-quartile range.

Lysholm scores will represent continuous data. Baseline and 3 months post 1st physiotherapy session scores will be described using descriptive statistics using mean and standard deviations if scores are normally distributed or median and inter-quartile range if data is skewed.

EQ-5D-5L scores will represent continuous data. Baseline and 3 months post 1st physiotherapy session scores will be described using descriptive statistics using mean and standard deviations if scores are normally distributed or median and inter-quartile range if data is skewed.

Patient satisfaction scores will be described using descriptive statistics. Ordinal data will be expressed using medians and inter-quartile ranges, and categorical data will be expressed as integers and percentages.

Baseline characteristics and additional outcome data on intervention delivery and harms will be expressed using descriptive statistics. Continuous variables will be described using means and standard deviations for normal distributions or medians and inter-quartiles range for non-normal distributions. Categorical data will be expressed as integers and percentages.

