### **SECTION 6.2 Harms**

#### **6.2a Adverse events**

For this study an adverse event (AE) will be described as any unfavourable sign or symptom related to completing the study intervention.

This study involves rehabilitation after a recent LPD. No additional risks are foreseen compared to usual rehabilitation at the John Radcliffe Trauma Outpatient Physiotherapy department.

Possible (expected) complications of rehabilitation are:

Newly acquired or temporary increases in knee pain and knee swelling; delayed onset muscle soreness, persistent patellar instability and recurrent patellar dislocation. Some of these may require the need for further surgery.

Symptoms such as delayed onset muscle soreness and increases in knee pain or swelling lasting less than 1 week that do not require medical attention will not be regarded as AEs, as these are common after commencing a new exercise regime post injury. These will be managed as outlined in section 4.3a and explained in the participation information booklet. In the unlikely event of a further patellar dislocation patients will be referred to the trauma and orthopaedic service for assessment and treatment. If physiotherapist become aware of any AEs while administering the intervention, whether the AE is related to the intervention will be determined by the physiotherapist and verified by *CF* in discussion with his supervisors. All AEs will be recorded on case report forms by the participant's physiotherapist.

AEs related to the intervention will also be recorded by participant reported questionnaire at 3 month follow-up.

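### For a participant who stops attending and does not reply, no step establishes re-dislocation or surgical-listing status up to 3 months, and section 5.3a sets no denominator for harms

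*Combined protocol and SAP*

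**What the plan says.** The Harms row of the table in section 5.1a covers "Patient and staff reported adverse events including any recurrent patellar dislocation, subsequent listing for knee surgery for mechanical instability", together with longer-lasting increases in pain or swelling caused by the exercises. Its window is "From beginning of intervention to 3 months post first physiotherapy session".

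Section 6.2a describes how these events reach the study. The physiotherapist completes a case report form, with the trigger worded as "If physiotherapist become aware of any AEs while administering the intervention". In addition, "AEs related to the intervention will also be recorded by participant reported questionnaire at 3 month follow-up". A participant who re-dislocates is sent to the trauma and orthopaedic service, but no step brings that information back to the study.

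Other sections bear on the point:

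- Section 6.2b has the participant's clinician complete a form for serious events between the start and the end of the exercise intervention.
- Section 5.1c provides at least one reminder for unreturned postal questionnaires. Section 5.1d provides attempted contact with people who withdraw or do not adhere.
- Section 5.2b says that the host trust "will collect information participant information from their medical records for this research study", without naming the items.
- On analysis, section 5.3a says: "Baseline characteristics and additional outcome data on intervention delivery and harms will be expressed using descriptive statistics". Categorical data become counts and percentages. Section 5.3b reports missing questionnaires and items.

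**The concern.** Section 4.4a defines attrition as not completing the 3-month data collection. Anyone counted as lost therefore also lacks the 3-month harms report. If that person has stopped attending as well, the physiotherapist route has closed, and harms status is unknown from last contact to 3 months.

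This matters most for re-dislocation and surgical listing. Both are discrete events that a hospital record would normally hold, and section 6.2a itself directs re-dislocations to the host trauma service. It is plausible, though the documents do not show it, that someone with either event would be more likely to leave physiotherapy. If so, the missing statuses would not be a random subset.

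Section 4.4b gives the purpose of recording harms as informing later research. A count that is incomplete by an unstated amount serves that purpose poorly. The authors have reason to expect losses: section 3.1b notes that in the one published trial comparing exercise programmes for this injury "there was an attrition rate of 52" per cent.

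**Working it through.** **Is there a figure to reproduce?** No. Section 4.6a says: "As this is a feasibility study, no power calculation has been performed. A sample size of 15 is a pragmatic choice". The harms analysis is descriptive, so the check concerns ascertainment and the arithmetic only gives scale.

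**Step 1. Take a participant who stops attending and does not reply, and test each route.**

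| Route | Section | Does it establish re-dislocation or listing status to 3 months? |
|---|---|---|
| Physiotherapist's case report form | 6.2a | Up to the last attended session only |
| 3-month questionnaire | 6.2a | No, not returned |
| Reminder | 5.1c | Only if it leads to a return |
| Contact attempt | 5.1d | Only if the person is reached and agrees; the stated aim is follow-up data in general |
| Serious event form | 6.2b | Serious events only, up to the end of the intervention, and only if the clinician knows; re-dislocation treated without admission, or a listing, need not qualify |
| Referral to the trauma service | 6.2a | A care pathway with no stated return of data |
| Medical records | 5.2b | Possible, but not tied to harms |

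No row gives a definite answer for this participant.

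**Step 2. How many could be affected?**

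Inputs: N = 15 (section 4.6a). Attrition is not assumed anywhere in the plan. The upper value used here is 52%, from the other trial cited in section 3.1b; the lower value of 20% is an assumption.

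- 0.20 × 15 = 3 without a 3-month harms report, 12 with one.
- 0.52 × 15 = 7.8, about 8 without, 7 with.

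Both overstate the number with no harms information, because people who attended some sessions were observed up to their last one.

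**Step 3. What does the choice of denominator do?**

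If no harm is recorded, the exact two-sided 95% upper limit is 1 − 0.025^(1/n):

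- n = 15: 21.8%
- n = 12: 26.5%
- n = 7: 41.0%

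These limits take the assessed participants as representative. Bounds that need no such assumption, for x participants with a recorded harm and m with unknown status, run from x/15 to (x + m)/15. With x = 1:

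- m = 3: 1/15 = 6.7% to 4/15 = 26.7%
- m = 8: 1/15 = 6.7% to 9/15 = 60.0%

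These are extremes, since they treat every lost participant as wholly unobserved.

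**Step 4. A second way for a listing to leave the count.**

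Section 5.1a makes listing for knee surgery for instability a harm. Section 4.2a makes listing for surgery before the intervention is complete an exclusion criterion. Section 5.1d lets the authors withdraw a participant later found not to meet the eligibility criteria. Read together, a listing during the intervention could be recorded as a harm or lead to the participant's removal. The plan does not say which, even for someone who is not lost.

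**The case against.** The strongest reply is that the plan does not hide the problem. Attrition is a primary outcome, questionnaire return has its own row in section 5.1a, and section 5.3b reports missing questionnaires. A reader of the results would see how many 3-month reports were absent. This stands. A reader might infer that the plan treats a missing report as absence of harm. The documents do not support that: section 5.3a sets no denominator at all, and understatement follows only if harms are shown over all enrolled.

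A reader might also infer that harms can be learned solely from the treating physiotherapist and the questionnaire. That too is stronger than the text, because the serious event form, reminders and contact attempts exist, and the Harms row refers to staff in general. What remains is that none of these settles status for someone who stops attending and does not reply.

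The figures can be called a worst case, and that is fair. The 52% is another trial's, the 20% is assumed, and partial observation is ignored. An example in which every event falls among the lost and none is noticed would show what is possible without estimating anything.

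Two practical objections shape the fix. Harms are defined in sections 4.4b and 6.2a as related to the intervention, and a hospital record cannot decide relatedness. Section 5.1d speaks of using data from before withdrawal, so a search of the records of someone who has fully withdrawn would go beyond it.

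Finally, this is a secondary, descriptive outcome in a single-group feasibility study that section 6.1 regards as minimal risk. That limits the importance of the point but does not remove it.

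**Conclusion.** The point holds as a gap in ascertainment and reporting. Followed as written, the plan can miss re-dislocations and surgical listings in participants who stop attending and do not reply, and it does not say over whom harms will be expressed.

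At an assumed attrition of 20% to 52%, 3 to 8 of 15 participants would lack the 3-month harms report, which is an upper bound on the gap at those rates. The direction and size of any bias cannot be derived from the documents: they depend on how many are lost, whether loss is related to harm, and which denominator is used. No primary outcome is affected. The change is worth making before enrolment because a stated secondary objective is weakened and the remedy is cheap.

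**What to change.** - **Sections 5.1a and 6.2a.** At each participant's 3-month date, check the host trust's records for index-knee re-dislocation, emergency or trauma re-attendance, and listing for knee surgery since the first session. Do this whether or not the questionnaire came back, so that ascertainment does not depend on reply. Leave out anyone who has withdrawn consent to further data collection or refused use of records. Pass events found this way through the existing relatedness review in section 6.2a.
- **Section 5.3a.** Report harms with the number assessed by each source as denominator. Show participants whose harms status is unknown after last contact as a separate category. This is needed even with the record check, which will not reliably capture pain or swelling.
- **Sections 4.2a, 5.1a and 5.1d.** Reconcile surgical listing as harm and as exclusion, and state that withdrawal for ineligibility does not remove a recorded listing from the harms count.

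The cost is at most 15 record checks and possibly a line in the information sheet, which is not among the documents reviewed. Section 7.1 describes ethical approval as still to be sought, so the change could go in with that submission; after approval, section 7.2 would apply. Events treated at other hospitals would still be missed.

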## 6.2b Serious adverse events

A serious adverse event (SAE) is any untoward medical occurrence that:

- Results in death,
- Is life-threatening,
- Requires inpatient hospitalisation or prolongation of existing hospitalisation,
- Results in persistent or significant disability/incapacity, or
- Consists of a congenital anomaly or birth defect.

Other “important medical events” may also be considered serious if they jeopardise the participant or require an intervention to prevent one of the above consequences. The term “life-threatening” in the definition of “serious” refers to an event in which the participant was at risk of death at the time of the event; it does not refer to an event which hypothetically might have caused death if it were more severe.

A SAE arising due to completion of the exercise intervention during this study is unlikely. If a SAE occurs during the period from commencing to finishing the exercise intervention, a SAE form must be completed by the participant’s clinician and forwarded to *CF* or one of his academic supervisors within 24 hours. *CF* in discussion with his supervisors *SH*, *MH* and *DK* will determine if the SAE is attributable to the intervention.

Only SAEs that are:

- Related to the study (i.e. they resulted from administration of any of the research procedures) and
- Unexpected (i.e. not listed in section 6.2a as an expected occurrence)

will be reported to the Research Ethics Committee (REC) who granted the study a favourable opinion approval and the study sponsor within 15 days of *CF* or his supervisors becoming aware of the event. It will be followed up until conclusion. If it is not deemed related to the intervention it will be recorded in the case report form.

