### **SECTION 4.3 Intervention**

All participants will receive the study intervention in addition to standard management of acute LPD by the trauma and orthopaedic service at the John Radcliffe hospital. Typically, this involves the provision of a lateral buttress splint and referral to physiotherapy with no limitations on weight-bearing or knee range of movement. Patients may receive advice on pain management, gait re-training and instruction of basic knee exercise from a member of the orthopaedic team or physiotherapist working in the NPC. No attempt will be made to modify this but what has been delivered in addition to the study intervention will be recorded in the study treatment logs to help characterise what acute care was delivered overall.

The intervention will be comprised of up to 6, one-to-one, physiotherapy sessions over a maximum duration of 3 months. 1 or 2 more sessions will be allowed only if deemed clinically essential. Additional sessions and the reasons for these will be recorded to understand if the intervention would need adapting for future studies. Less than 6 physiotherapy sessions can be agreed with the participant if they are self-managing effectively and their goals have been achieved, (these stopping rules will be recorded). A treatment duration of up to 3 months is representative of current care in the NHS for first-time LPD. Initial physiotherapy sessions will be 45-60 minutes and subsequent physiotherapy sessions will be 30 minutes as per local practice.

The exercise intervention has been designed to address the biomechanics associated with the LPD mechanism of injury, improve common lower limb strength deficits in this patient population and facilitate a return to the participant's desired activities which may include activities such as running, hopping and twisting.

The LPD mechanism of injury is thought to result from a quadriceps contraction with the knee in a position of slight knee flexion, femoral internal rotation and tibial external rotation which forces the patella laterally. This is supported by studies demonstrating peak lateral displacement of the patella at angles of 0-30° knee flexion in patients with patellofemoral

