- Harms. For this study harms will be defined as any unfavourable sign or symptom related to completing the study intervention. The recording of harms has been recommended in feasibility studies to inform future research design and processes. This will be measured from commencement of the intervention to 3 month follow-up as outlined in section 6.2a.
- Determine what assessment findings are consistent with a diagnosis of LPD. A member of the trauma and orthopaedic team will be required to assess the presence/absence of proposed assessment findings to include in the eligibility criteria for future studies as outlined in section 5.1. This will inform the feasibility of using these assessment findings in the eligibility criteria for future studies.

- Intervention delivery. Treatment logs will be analysed to record the duration from injury to commencing the intervention, the number of physiotherapy sessions received by participants, the duration of intervention and the exercises prescribed.

Additional demographic data will be collected as part of the study. Further information on this and the time points for data collection are outlined in section 5.1

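### The SAE form is required only until a participant finishes the exercises, while harms are measured to 3 months, so serious events after an early finish need no form or attribution review

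*Combined protocol and SAP*

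**What the plan says.** **Harms outcome.** The harms row of the table in section 5.1a gives the time frame as "From beginning of intervention to 3 months post first physiotherapy session". Its content is "Patient and staff reported adverse events including any recurrent patellar dislocation, subsequent listing for knee surgery for mechanical instability", together with exercise-related increases in pain or swelling that last more than a week. Section 4.4b gives the same window and points to 6.2a for the method: "This will be measured from commencement of the intervention to 3 month follow-up as outlined in section 6.2a".

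**Adverse events.** Section 6.2a defines an AE as "any unfavourable sign or symptom related to completing the study intervention". Physiotherapists record the AEs they become aware of while delivering treatment. In addition, "AEs related to the intervention will also be recorded by participant reported questionnaire at 3 month follow-up".

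**Serious adverse events.** Section 6.2b opens with "A serious adverse event (SAE) is any untoward medical occurrence that" and then lists the usual seriousness criteria, with no condition of relatedness. The duty to complete a form applies "If a SAE occurs during the period from commencing to finishing the exercise intervention". The participant's clinician sends the form within 24 hours, and the investigator and supervisors decide on attribution. Related and unexpected SAEs go to the ethics committee and sponsor within 15 days of awareness; unrelated ones are noted in the case report form.

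**When treatment can end.** Section 4.3 caps treatment at 3 months and allows an earlier end: "Less than 6 physiotherapy sessions can be agreed with the participant if they are self-managing effectively and their goals have been achieved". Section 5.1d anticipates withdrawal and non-adherence.

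**The concern.** The harms outcome has the same 3-month window for every participant. The SAE form has a window that depends on when each participant stops treatment. Nothing in the text reconciles the two, and the word that sets the cut-off is undefined: it could mean the last session, formal discharge or the end of home exercise.

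The people affected are those discharged early because their goals were met, who may be resuming demanding activity, and those who stop attending, possibly because of a problem. Once their treatment ends, the plan no longer requires a prompt report of a serious event or a decision on whether the intervention caused it. Harms are a secondary outcome in a study of 15 people, so one serious event that is missed, or recorded without attribution, would change the safety summary. Section 6.1 says there will be no data monitoring committee, so the SAE form is the main route by which a serious event reaches those overseeing the study.

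**Working it through.** The documents give no figure to reproduce. The check sets the windows and routes side by side and then illustrates the size of the gap.

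**1. Windows**

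| Item | Starts | Ends | Source |
|---|---|---|---|
| Harms outcome | Start of intervention | 3 months after first session | 4.4b, 5.1a |
| SAE form, 24 hours, attribution | Start of intervention | Finish of intervention (undefined) | 6.2b |

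The end points coincide only for someone treated for the full 3 months. Sections 4.3 and 5.1d both allow an earlier end.

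**2. Routes that remain after an early finish**

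- *Staff reports.* The harms row includes them to 3 months. However, 4.4b refers to 6.2a for the method, and the staff route there operates while treatment is being delivered. No staff procedure is described after discharge.
- *Questionnaire at 3 months.* Section 6.2a limits it to AEs related to the intervention. An SAE under 6.2b carries no such limit, and attribution belongs to the study team. After treatment ends, the participant in effect makes the first judgement of relatedness.
- *Named harms items.* Recurrent dislocation and listing for knee surgery for mechanical instability are in the harms row to 3 months. They are therefore within the outcome after discharge, although the general AE definition leaves some doubt about whether they must be related.
- *Follow-up effort.* Section 5.1c gives postal non-responders at least one reminder by telephone or email. Under 5.1d the investigator tries to contact people who withdraw or do not adhere, to ask whether they will give follow-up data. Section 5.1c also means that anyone whose last appointment is not within a week of the 3-month point is followed by post, so early finishers depend on a returned form.

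**3. What has no route**

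A serious event that the participant considers unrelated, and that is not a named item, has no stated route once treatment has ended. Nor does a death. Yet 6.2b intends unrelated SAEs to be recorded.

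**4. Size of the gap (illustration)**

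Take 3 months as 13 weeks and let *w* be the week of finishing. Gap = 13 − *w* weeks; share of the harms window = (13 − *w*)/13.

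- *w* = 7: 13 − 7 = 6 weeks; 6/13 = 46%
- *w* = 10: 13 − 10 = 3 weeks; 3/13 = 23%
- *w* = 13: no gap

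Week 7 is the lower end of the average NHS duration quoted in section 3.1a for first-time dislocation. Week 10 is an assumption. These are shares of time, not of events missed.

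**The case against.** A reader might infer that serious events after early discharge or drop-out go uncaptured altogether. The documents do not support that. The harms row names recurrent dislocation and surgery listing to 3 months for everyone, the questionnaire asks about related AEs, and 5.1c and 5.1d provide reminders and contact attempts. Nor does the text say that the questionnaire covers only events someone has already adjudicated as related. The questionnaire itself is not in the documents, so its exact wording is unknown.

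Other points on this side also stand. The study has one arm, its analysis is descriptive and no SAE rate is planned, so unequal windows bias no comparison. The protocol calls an SAE due to the exercises unlikely and the risk minimal. Recurrent dislocation is listed as expected in 6.2a, so even an SAE form for it would not lead to a report to the ethics committee under 6.2b. The 7-week figure describes usual care for first-time dislocation. The study also enrols recurrent cases, whose usual duration section 3.1a says is unknown. Finally, a longer window does not by itself tell the study team about an event in someone they no longer see.

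These points limit the consequence but do not remove the mismatch. The self-report route is retrospective and depends on response; section 3.1b cites 52% attrition in the one published randomised comparison of exercise programmes. It also has no 24-hour step, and the 15-day clock in 6.2b starts only at awareness, which a questionnaire could delay by weeks.

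**Conclusion.** The point holds in a limited form. For a participant who finishes or stops before 3 months, the plan drops the SAE form, the 24-hour limit and the attribution review tied to it, although the harms outcome continues. Related events and the named items can still be picked up by self-report. Other serious events and deaths have no stated route.

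The size depends on when participants finish, which the documents do not predict: 46% of the harms window for a finish at week 7, and nothing for a finish at 3 months, taking 3 months as 13 weeks. If finishing is read as the end of home exercise and not as the last session, the gap could be smaller; the text does not settle this. The mismatch should be corrected, but it does not threaten the feasibility objectives.

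**What to change.** Reconcile sections 4.4b, 5.1a, 6.2a and 6.2b as follows.

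1. In 6.2b, replace the reporting period with: *from the first physiotherapy session to 3 months after it, whether or not treatment has been completed*. This also removes the need to define finishing.
2. Add one neutral item to the existing 3-month questionnaire and to the reminder contact, asking about any hospital attendance or re-dislocation since the first session, not limited to events thought to be related.
3. State that an SAE form is completed, with attribution decided as now, whenever the study team learns of a serious event in that window.
4. Report SAEs over the window for all participants, and give the number with no 3-month response.

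The cost is a sentence or two in 6.2b, one questionnaire item and a few extra forms. Section 7.1 says ethical approval is still to be sought; if the change comes after approval, it may be a substantive amendment under section 7.2. Non-responders will remain only partly covered, which is why their number should be reported beside the SAE count.
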